7.3 DOES THIS STUDY INVOLVE MORE THAN MINIMAL RISK TO STUDY PARTICIPANTS?

Minimal risk means that the probability and magnitude of harm or discomfort anticipated in the research are not greater in and of themselves than those ordinarily encountered in daily activities or during the performance of routine physical or psychological examinations or tests. Examples of research involving greater than minimal risk include collecting data about abuse or illegal activities. Note: if the project qualifies for Exempt review (http://www.irb.vt.edu/pages/categories.htm), it will not need to go to the Full Board.

No	9
☐ Yes	
PROJECT'S APPL	ED "YES" TO ANY ONE OF THE ABOVE QUESTIONS, 7.1, 7.2, OR 7.3, THE BOARD MAY REVIEW THE ICATION MATERIALS AT ITS MONTHLY MEETING. VIEW THE FOLLOWING LINK FOR DEADLINES IL INFORMATION: http://www.irb.vt.edu/pages/deadlines.htm
Section 8: C	Confidentiality / Anonymity
For more information	on about confidentiality and anonymity visit the following link: http://www.irb.vt.edu/pages/confidentiality.htm
ANYONE OUT For example – to the $\Box^{\mathbf{No}}$	SONALLY IDENTIFYING STUDY RESULTS OR DATA BE RELEASED TO SIDE OF THE RESEARCH TEAM? The funding agency or outside data analyst, or participants identified in publications with individual consent
number) may be	ill identifying data be released? Participant's identifying information (e.g., name, address, phone released to the VTC administrative offices and the VT Controller's office in order to process eimbursements for participant payments.
NAME, CONTA	STUDY FILES CONTAIN PARTICIPANT IDENTIFYING INFORMATION (E.G., ACT INFORMATION, VIDEO/AUDIO RECORDINGS)? ignatures on a consent form, select "Yes."
No, go to question	on 8.3
	stions within table
	IF YES
	Describe if/how the study will utilize study codes: Using only ID numbers and initials and keeping

If applicable, where will the key [i.e., linked code and identifying information document (for instance, John Doe $= study \ ID \ 001$)] be stored and who will have access? Master files linking subject names to study ID numbers will be accessible only to trained study team members delegated this access by the PI.

all data in locked offices will protect confidentiality. Computer databases will have coded

identifiers and all computers will be password protected.

Note: the key should be stored separately from subjects' completed data documents and accessibility should be limited.

The IRB strongly suggests and may require that all data documents (e.g., questionnaire responses, interview responses, etc.) do not include or request identifying information (e.g., name, contact information, etc.) from participants. If you need to link subjects' identifying information to subjects' data documents, use a study ID/code on all data documents.

10

8.3 WHERE WILL DATA BE STORED?

Examples of data - questionnaire, interview responses, downloaded online survey data, observation recordings, biological samples

All data and participant binders will be stored in a safe place to protect confidential participant information. Safe places will include locked filing cabinets or locked rooms accessible only to study personnel. The full

names of participants will not be listed on the outside of binders to protect confidentiality of study participants.

Electronic data will be saved in secure, limited access shared drives on password-protected computers accessible only to the research team.

8.4 WHO WILL HAVE ACCESS TO STUDY DATA?

Access to study data will be limited to study personnel who have completed the Virginia Tech IRB Human Subjects Tutorial and who have been delegated the responsibilties of data collection, management, or analyses by the PI.

8.5 DESCRIBE THE PLANS FOR RETAINING OR DESTROYING THE STUDY DATA

Data collected from this study will be retained and destroyed in accordance with the center's policy that requires a 3-year retention period following final publication of the data.

8.6 DOES THIS STUDY REQUEST INFORMATION FROM PARTICIPANTS REGARDING ILLEGAL BEHAVIOR?

\square No, go to question	19.1
	tions within table
	IF YES

Does the study plan to obtain a Certificate of Confidentiality?	
⊠ No	
☐ Yes (Note: participants must be fully informed of the conditions of the Certificate of Confidentiality	
within the consent process and form)	
For more information about Certificates of Confidentiality, visit the following link: http://www.irb.vt.edu/pages/coc.htm	

Section 9: Compensation

For more information about compensating subjects, visit the following link: http://www.irb.vt.edu/pages/compensation.htm

9.1 WILL SUBJECTS BE COMPENSATED FOR THEIR PARTICIPATION?

No, go to question 10.1

∀es, answer questions within table

What is the amount of compensation? Compensation for participation will be as

follows: \$20.00 for completion of informed consent

\$30.00 for the assessment session

11

\$1.00 for each day the participant responds to the Interactive Voice Response system (x7 total days)

\$20.00 for the Hypothetical Experimental Tobacco Marketplace session **\$10.00** completion bonus

Combined, the subjects could be compensated approximately up to \$87 by completing all aspects of the experiment.

To allow for payments that are both convenient and rapidly available, we may pay participants with reloadable prepaid cards through Greenphire ClinCard (www.greenphire.com), an FDIC insured payment provider that specializes in clinical trial stipend payments that comply with IRB privacy regulations and considerations. At the beginning of the study, the participant will receive a prepaid MasterCard debit card that can be used anywhere that accepts MasterCard. As payments are earned in the course of the study, additional funds will be added to the account for that participant. Funds are immediately available when added and participants can check their balance as desired. This system will allow frequent, immediately available payments. Payments may also be made via check, however remote debit card payments will be used most often.

Will compensation be prorated? Yes, please describe: Subjects he/she has completed.	will be compensated based on what study procedures
\square No, explain why and clarify whe	ther subjects will receive full compensation if they withdraw from
the study?	
Payment must not be contingent upo	ompensation should be prorated based on duration of study participation. n completion of study procedures. In other words, even if the subject he/she should be compensated, at least partially, based on what study

Section 10: Audio / Video Recording

For more information about audio/video recording participants, visit the following link:

http://www.irb.vt.edu/pages/recordings.htm 10.1 WILL YOUR STUDY INVOLVE VIDEO AND/OR AUDIO

RECORDING?

$ \boxtimes$ No , go to question 11.1	
☐ Yes , answer ques	stions within table
	IF YES
	This project involves:
	☐ Audio recordings only
	☐ Video recordings only
	☐ Both video and audio recordings
	Provide compelling justification for the use of audio/video recording:

How will data within the recordings be retrieved / transcribed?
How and where will recordings (e.g., tapes, digital data, data backups) be stored to ensure security?
Who will have access to the recordings?
Who will transcribe the recordings?

When will the recordings be erased / destroyed?	
	- 1

Section 11: Research Involving Students

11.1 DOES THIS PROJECT INCLUDE STUDENTS AS PARTICIPANTS?

No, go to question	\square No, go to question 12.1	
☐ Yes , answer ques	stions within table	
	IF YES	
	Does this study involve conducting research with students of the researcher?	
	□ No	
	☐ Yes, describe safeguards the study will implement to protect against coercion or undue influence for participation:	
	Note: if it is feasible to use students from a class of students not under the instruction of the researcher, the IRB recommends and may require doing so.	
	Will the study need to access student records (e.g., SAT, GPA, or GRE scores)?	
	□ No	
	□ Yes	
11.2 DOES THI	S PROJECT INCLUDE ELEMENTARY , JUNIOR , OR HIGH SCHOOL STUDENTS?	
No, go to question		
☐ Yes, answer ques	stions within table	
	IF YES	
	Will study procedures be completed during school hours?	
	□ No	
	☐ Yes	
	If yes,	

	Students not included in the study may view other students' involvement with the research during time as unfair. Address this issue and how the study will reduce this outcome:
	Missing out on regular class time or seeing other students participate may influence a student's decision participate. Address how the study will reduce this outcome:
	Is the school's approval letter(s) attached to this submission?
	☐ Yes
	☐ No, project involves Montgomery County Public Schools (MCPS)
	□ No, explain why:
	You will need to obtain school approval (if involving MCPS, click here: http://www.irb.vt.edu/pages/mcps.htm). Approval is typically granted by the superintendent, principal, and classroom teacher (in that order). Approval by an individual teacher is insufficient. School approval, in the form of a letter or a memorandum should accompany the approval request to the IRB.
•	
11.3 DOES THI	S PROJECT INCLUDE COLLEGE STUDENTS?
No, go to question	12.1
☐ Yes , answer quest	tions within table
	IF YES
	Some college students might be minors. Indicate whether these minors will be included in the research or actively excluded:
	☐ Actively excluded, describe how the study will ensure that minors will not be included:
	Will extra credit be offered to subjects?
	□ No
	□ Yes
	If yes,
	What will be offered to subjects as an equal alternative to receiving extra credit without participating this study?
	Include a description of the extra credit (e.g., amount) to be provided within question 9.1 ("IF YES" table)

12.1 DOES THIS PROJECT INVOLVE MINORS (UNDER THE AGE OF 18 IN VIRGINIA)?

Note: age constituting a minor may differ in other States.

No, go	to question 13.1	

1	4

☐ **Yes,** answer questions within table

IF YES	
Does the project reasonably pose a risk of reports of current threats of abuse and/or	
suicide? No	
\square Yes, thoroughly explain how the study will react to such reports:	
Note: subjects and parents must be fully informed of the fact that researchers must report threats of suicide suspected/reported abuse to the appropriate authorities within the Confidentiality section of the Consent, Assent, and/or Permission documents.	or
Are you requesting a waiver of parental permission (i.e., parent uninformed of child's	
involvement)? No, both parents/guardians will provide their permission, if possible.	
☐ No, only one parent/guardian will provide permission.	
☐ Yes, describe below how your research meets all of the following criteria (A-D): Criteria A - The research involves no more than minimal risk to the subjects:	
Criteria B - The waiver will not adversely affect the rights and welfare of the subjects:	
Criteria C - The research could not practicably be carried out without the waiver:	
Criteria D - (Optional) Parents will be provided with additional pertinent information after	
Is it possible that minor research participants will reach the legal age of consent (18 in Virginia) while enrolled in this study?	
□ No	
Yes, will the investigators seek and obtain the legally effective informed consent (in place of the minors' previously provided assent and parents' permission) for the now-adult subjects for any ongoing interactions with the subjects, or analysis of subjects' data? If yes, explain how:	
For more information about minors reaching legal age during enrollment, visit the following link: http://www.irb.vt.edu/pages/assent.htm	
The procedure for obtaining assent from minors and permission from the minor's guardian(s) must be described in Section 4 (Consent Process) of this form	

Section 13: Research Involving Deception

For more information about involving deception in research and for assistance with developing your debriefing form, visit our website at http://www.irb.vt.edu/pages/deception.htm

13.1 DOES THIS PROJECT INVOLVE DECEPTION?

☐ Yes , answer que	estions within table
	IF YES
	Describe the deception:
	15
	Why is the use of deception necessary for this project?
	Describe the debriefing process:
	Provide an explanation of how the study meets all the following criteria (A-D) for an alteration of Criteria A - The research involves no more than minimal risk to the subjects: Criteria B. The elteration will not adversely effect the rights and welfare of the
	Criteria B - The alteration will not adversely affect the rights and welfare of the subjects: Criteria C - The research could not practicably be carried out without the
	alteration:
	Criteria D - (Optional) Subjects will be provided with additional pertinent information after participation debriefing for studies involving deception):
	By nature, studies involving deception cannot provide subjects with a complete description of the study during the consent process; therefore, the IRB must allow (by granting an alteration of consent) a consent process which does not include, or which alters, some or all of the elements of informed consent.
	The IRB requests that the researcher use the title "Information Sheet" instead of "Consent Form" on the document used to obtain subjects' signatures to participate in the research. This will adequately reflect the fact that the subject cannot fully consent to the research without the researcher fully disclosing the true intent of the research.
Section 14:	Research Involving Existing Data
	HIS PROJECT INVOLVE THE COLLECTION OR STUDY/ANALYSIS OF EXISTING MENTS, RECORDS, PATHOLOGICAL SPECIMENS, OR DIAGNOSTIC
Please note: it is no	ot considered existing data if a researcher transfers to Virginia Tech from another institution and will be nalysis of an on-going study.
No, you are fini	shed with the application
☐ Yes , answer que	estions within table

IF YES
From where does the existing data originate?
Provide a detailed description of the existing data that will be collected or studied/analyzed:
Is the source of the data public?
\square No, continue with the next question
\square Yes, you are finished with this application
Will any individual associated with this project (internal or external) have access to or be provided with
existing data containing information which would enable the identification of subjects: • Directly (e.g., by name, phone number, address, email address, social security number, student ID number), or
■ Indirectly through study codes even if the researcher or research team does not have access to the master list linking study codes to identifiable information such as name, student ID number, etc or
. Indirectly through the use of information that could reasonably be used in combination to identify an individual (e.g., demographics)
16

☐ No, collected/analyzed data will be completely de-identified
\square Yes,
If yes,
Research will not qualify for exempt review; therefore, if feasible, written consent must be obtained from individuals whose data will be collected / analyzed, unless this requirement is waived by the IRB.
Will written/signed or verbal consent be obtained from participants prior to the analysis of collected data?

This research protocol represents a contract between all research personnel associated with the project, the University, and federal government; therefore, must be followed accordingly and kept current.

Proposed modifications must be approved by the IRB prior to implementation except where necessary to eliminate apparent immediate hazards to the human subjects.

Do not begin human subjects activities until you receive an IRB approval letter via email.

It is the Principal Investigator's responsibility to ensure all members of the research team who interact with research subjects, or collect or handle human subjects data have completed human subjects protection training prior to interacting with subjects, or handling or collecting the data.

-----END-----

## **Statistical Analysis Plan**

Participants' characteristics, including demographics and smoking-related assessments collected at a baseline session, were described using mean, standard deviation, and percentages, where appropriate. The perceived risk of HVCs was compared to the perceived risk of LVCs using a paired t-test.

Purchasing cigarettes (LVCs and HVCs) is a continuous measure, ie, the number of cigarettes purchased. In practice, participants opted to purchase either LVCs or HVCs and rarely purchased both products in the same trial (11.94% of the trials). As a result, we opted to model the purchasing of cigarettes and alternative tobacco products as a binary indicator; whether or not a participant purchased that type of cigarette in a trial. The purchasing of HVCs was estimated using a mixed-effects logistic regression to model the association between session, ventilation level (30.6% or 22.0% ventilation), and price of a HVC with a random effect for each participant due to the repeated (3) measurements study design. Similarly, the purchasing of LVCs and alternative tobacco products was estimated using a mixed-effects logistic regression to model the association between session, ventilation level (3.0% or 11.6% ventilation), and price of HVCs. Note that we included a variable for ventilation level in both models to quantify if the changes in product specifications over time influenced the overall purchasing patterns.

The proportion of the total budget spent on cigarettes was estimated using a repeated measures analysis of variance (RMANOVA) to evaluate the session's role and the price of HVCs. The total number of cigarettes purchased was also modeled using an RMANOVA, including the session and price of HVCs as independent variables. For these analyses, the price of cigarettes was categorical. Post hoc comparisons were performed using Tukey's correction for multiple testing.

For all analyses, the inclusion of the interaction between session and price of an HVC was determined by the model with the lowest Bayesian Information Criteria (BIC). After model selection, the final model to predict the total quantity of cigarettes purchased included the interaction between session and price, and the final model for all other outcome measures did not include this interaction. R software Version 3.5.1 was used for all data analysis (R Core Team, 2021). All statistical tests were considered significant at the < 0.05 level.

A post hoc power analysis was performed with 1000 simulations using the package SIMR (Green & MacLeod, 2016). This analysis set the effect size to the smallest observed value in the results

(OR: 2.8; Purchasing patterns of low-ventilation cigarettes section). Using this effect size, the sample size of 20 participants, and an alpha of 0.05, we achieved 88% power in this study.

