A fundamental observation of economics is that the type and number of products in a marketplace can alter a commodity's demand elasticity as well as the type and degree of interaction among those products. As a result, the ability to achieve the tobacco control goals of reducing the consumption of a particular product may be enhanced or diminished via the economic processes of substitution and complementarity (see Bickel, DeGrandpre, et al., 1995 for a review). Substitution, complementarity, and independence are measured by cross-price elasticity of demand and are represented by elasticity slopes that are positive, negative, or near zero, respectively. Studies to date have almost exclusively examined only pairs of products and in very few cases three concurrent commodities. Relevant to this application, the investigators examined the interaction of three commodities in one of their prior studies (Johnson, et al., 2004). Specifically, smokers had access to conventional cigarettes, reduced-nicotine cigarettes, and nicotine gum. When the price of conventional cigarettes increased, consumption of both reduced-nicotine cigarettes and nicotine gum increased even though their prices were fixed. Thus, reduced-nicotine

cigarettes and nicotine gum functioned as substitutes for conventional cigarettes. Indeed, by concurrently using both products, the smoker could reproduce different aspects of the conventional cigarette experience by consuming the reduced-nicotine cigarette (i.e., sensory effects associated with combustible tobacco smoke inhalation) and nicotine gum (i.e., central effects associated with nicotine ingestion). Importantly, reduced-nicotine cigarettes functioned as a better substitute than gum when each was offered as a substitute alone (the use of denicotinized cigarettes increased the most).

To inform how various products may interact, we have developed and tested a novel method called the Experimental Tobacco Marketplace. The Experimental Tobacco Marketplace is a systematic extension of similar marketplace methods used with other consumer products (e.g., food marketplaces used in obesity and other nutrition-related research; Epstein, Dearing, Roba, & Finkelstein, 2010). In experimental

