marketplaces, multiple products are available and the experimenter controls the prices for each. These marketplaces can be either physical or virtual stores (similar to online retailers) and permit the examination of demand elasticity and intensity and degree of substitution or complementarity in consumer behavior under conditions that approximate naturalistic settings.

This study will extend findings from an ongoing project examining the effects of different concentrations of nicotine in cigarettes (0.4mg/g, 1.4mg/g, 2.5mg/g, 5.6mg/g, 17.4mg/g) on laboratory behavioral economic demand measures by including nicotine pouches (a novel product) and utilizing a within-subjects design. Employing this innovative Experimental Tobacco Marketplace, we propose to examine 2 concentrations of reduced-nicotine cigarettes (0.4 mg/g, 17.4mg/g) and tobacco-free nicotine pouches (2 mg and 8 mg). We will use a within-subjects design to allow smokers to sample each of the high dose and low dose cigarettes as well as a high dose and low dose of commercially available tobacco-free nicotine pouches. After sampling, participants will complete one Experimental Tobacco Marketplace session under four conditions: 1) increasing prices for the 0.4 mg/g cigarette with no other products available; 2) increasing prices for the 17.5 mg/g cigarette with no other products available; and 4) increasing prices for the 17.5 mg/g cigarette with other products available. The results of this experiment will be valuable in determining the degree and extent to which cigarette smokers may switch to a harm reduction alternative.

2.2 EXPLAIN WHAT THE RESEARCH TEAM PLANS TO DO WITH THE STUDY RESULTS:

For example - publish or use for dissertation

The research team intends to publish the results of the current study in peer-reviewed journals.

Section 3: Recruitment

3.1 DESCRIBE THE SUBJECT POOL, INCLUDING INCLUSION AND EXCLUSION CRITERIA AND NUMBER OF SUBJECTS:

Examples of inclusion/exclusion criteria - gender, age, health status, ethnicity

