Hypothetical Experimental Tobacco Marketplace sessions (approximately 15-30 min). Approximately 7 days following the completion of the sampling period, participants will return to the laboratory where they will bring back SPECTRUM cigarette butts and any unused products. We will ask them to complete a Hypothetical Experimental Tobacco Marketplace. During these Hypothetical Experimental Tobacco Marketplace sessions, participants will sit in front of a computer and respond to an online marketplace where they will be able to "purchase" a variety of nicotine products (e.g., investigational cigarettes, nicotine gum, snus, nicotine pouches). Importantly, the marketplace interface mimics what participants might encounter if they shopped online for these products. In order to obtain the behavioral economic measures described earlier (e.g., demand intensity, substitutability, complementarity), participants will complete a series of purchasing scenarios where the price of cigarettes (investigational cigarettes) is manipulated (approximately 6 prices) and all other nicotine products remain at a constant price. Participants will be given an allowance equal to seven days' worth of their typical expenditure on cigarettes and/or other tobacco products and will be asked to make purchases for the following seven days. Participants will be told to make these decisions as if they will actually receive the products, but participants will not actually receive the products they purchase.

The Hypothetical Experimental Tobacco Marketplace sessions will include:

- 1.Investigational cigarette A (0.4mg/g) increases in price (across separate blocks), with no other products available
- 2.Investigational cigarette B (17.4 mg/g) increases in price (across separate blocks), with no other products available
- 3. Investigational cigarette A (0.4mg/g) increases in price (across separate blocks), all other products' prices stay the same (no conventional cigarettes).
- 4.Investigational cigarette B (17.4 mg/g) increases in price (across separate blocks), all other products' prices stay the same (no conventional cigarettes).

During the last session, participants will complete several of the tasks completed during the assessment session (e.g., cigarette and nicotine pouch valuation, delay discounting tasks for hypothetical money, Timeline Followback, Fagerström Test of Cigarette Dependence).

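### The SAP's bought/not-bought model for alternative products cannot tell adding an alternative from replacing cigarettes, and its two quantity analyses address replacement only in aggregate

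*SAP*

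**What the plan says.** Protocol section 2.1 says the results will help in "determining the degree and extent to which cigarette smokers may switch to a harm reduction alternative". The same section names the measure: "Substitution, complementarity, and independence are measured by cross-price elasticity of demand". Section 5.1 sets out four hypothetical marketplace conditions. In conditions 1 and 2 one investigational cigarette (0.4 or 17.4 mg/g) is the only product on sale. In conditions 3 and 4 other products are offered at constant prices while the cigarette's price rises over about 6 levels. The budget is set by the line that begins "Participants will be given an allowance equal to seven days" and is tied to usual tobacco spending.

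The SAP (section Statistical Analysis Plan) reduces purchases to yes or no: "we opted to model the purchasing of cigarettes and alternative tobacco products as a binary indicator; whether or not a participant purchased that type" in a trial. The reason given is that participants "rarely purchased both products in the same trial (11.94% of the trials"). The two products there are low- and high-ventilation cigarettes (LVCs and HVCs). For the other products, "the purchasing of LVCs and alternative tobacco products was estimated using a mixed-effects logistic regression", with session, ventilation level and HVC price as predictors. The section then adds two quantity outcomes, each analysed by session and HVC price: "The proportion of the total budget spent on cigarettes was estimated using a repeated measures analysis of variance", and "The total number of cigarettes purchased was also modeled using an RMANOVA".

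**The concern.** Switching concerns two products jointly: less of one because of the other. The alternative-product model looks at one product alone. It has no category for what else was bought, no term for cigarettes bought in the same trial, and no quantity of the alternative. A trial with pouches plus a full week of cigarettes has the same outcome value as a trial with pouches and no cigarettes.

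The stated reason for the binary outcome does not cover this. Rare joint purchase of two cigarette types says nothing about how often a cigarette and an alternative are bought together, and no figure for that is given.

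At stake is how a rise in alternative purchasing with cigarette price is read. It could be replacement, add-on use or a mixture, and the model's odds ratio would not show which.

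**Working it through.** **Plan's own figure.** The 11.94% cannot be recomputed, because the trial counts are not given. It concerns HVC with LVC, so it supplies no input here. The SAP's post hoc power of 88% plays no part in this point.

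**Step 1: what separate indicators can show.** Let pC be the proportion of trials with any cigarette bought and pA the proportion with any alternative bought. The share with alternatives and no cigarettes satisfies

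max(0, pA − pC) ≤ P(alternative, no cigarette) ≤ min(pA, 1 − pC).

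The documents give neither proportion, so these rates are assumptions:

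| pC | pA | Lower bound | Upper bound |
|---|---|---|---|
| 0.60 | 0.50 | max(0, −0.10) = 0% | min(0.50, 0.40) = 40% |
| 0.50 | 0.50 | max(0, 0) = 0% | min(0.50, 0.50) = 50% |
| 0.40 | 0.60 | max(0, 0.20) = 20% | min(0.60, 0.60) = 60% |

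The width depends on the rates. In the third row some complete switching is certain.

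**Step 2: partial replacement.** Take an assumed smoker of 140 cigarettes a week who buys an alternative and then 140, 70, 10 or 0 cigarettes. The alternative indicator is 1, 1, 1, 1 and the any-cigarette indicator is 1, 1, 1, 0. Only full replacement changes an indicator. The SAP's total-cigarettes outcome does separate the four cases.

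**Step 3: what total cigarettes and budget share add.** With a fixed allowance, price alone can cut quantity. An assumed $100 buys 100 cigarettes at $1 and 25 at $4. The total falls by 75%, the cigarette share stays at 100%, and no alternative has been bought. Budget share rightly shows no shift in this case.

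**Step 4: all the outcomes together.** Take ten trials with an assumed $120 allowance, cigarettes at $1, and 100 cigarettes as the reference. Assume that money may be left unspent; the documents do not say otherwise.

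- Pattern A: five trials with 50 cigarettes plus an alternative, and five with 100 cigarettes and no alternative.
- Pattern B: five trials with 50 cigarettes and no alternative, and five with 100 cigarettes plus an alternative costing at most $20.

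In both patterns the any-cigarette rate is 10/10 and the alternative rate is 5/10. Mean cigarettes are (5×50 + 5×100)/10 = 75, and mean budget share is 75/120 = 62.5%. The SAP's outcomes agree throughout. Yet in A the alternative goes with a halving of cigarettes, and in B it is purely added. Mean cigarettes among trials with both products would separate them: 50 in A, 100 in B.

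**Step 5: the protocol's measure.** Cross-price elasticity is the percentage change in the quantity of the alternative divided by the percentage change in cigarette price. The SAP analyses no quantity of the alternative, so none of its outcomes is this measure.

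**The case against.** The strongest reply is that the binary indicator is not the whole analysis. Total cigarettes and cigarette budget share are in the same SAP section. Pure add-on use leaves the total unchanged, while replacement lowers it. Under a fixed allowance, money moved to alternatives lowers the cigarette share. Complete replacement also appears as a zero in the cigarette indicators. All of this stands. A reader might infer that the plan carries no information on replacement, or that every result on alternatives could be add-on use. The documents do not support that. What remains is the missing link within a trial (step 4) and the missing quantity of the alternative (step 5).

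Three further limits also stand:

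- The protocol's sentence on switching is a rationale, and the SAP draws no conclusion about switching. It cannot be said that the plan makes an unsupported claim.
- The protocol speaks of degree and extent, which is graded. Treating alternatives-only as the sole form of switching would put a fall from 140 cigarettes to 10 in the same class as no fall at all.
- The SAP concerns cigarette ventilation in 20 participants and does not mention pouches or nicotine content. The protocol concerns nicotine content and pouches in up to 100 smokers. The SAP's model therefore cannot be carried over to conditions 3 and 4 unchanged. This mismatch is the larger problem, but it does not remove this one: no analysis in the supplied SAP separates adding from replacing.

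**Conclusion.** The point holds in limited form and should be addressed. The alternative-product model scores adding and replacing alike, and the 11.94% does not justify that. The two repeated-measures analyses narrow the gap without closing it. Neither ties fewer cigarettes to an alternative bought in the same trial, and neither is the substitution measure that the protocol names.

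The size cannot be fixed from the documents. Under the assumed rates, the share of trials with complete switching is known only to within 40 to 50 percentage points. A reader might infer that identical separate results are always compatible with no switching. The third set of rates, with its floor of 20%, shows that they are not. The bounds use the indicators alone; the quantity outcomes add information that they leave out. Step 4 also assumes that the allowance need not be fully spent.

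**What to change.** For the scenarios in which alternatives are on sale (protocol section 5.1, conditions 3 and 4):

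1. Classify each price trial as cigarettes only, both, alternatives only or neither. Tabulate the four classes by price and cigarette type.
2. Model alternatives-only, labelled as complete switching, in a mixed-effects logistic model. Use price and cigarette nicotine content as terms, in place of the SAP's ventilation and HVC-price terms, which do not exist in these conditions.
3. Report cigarette and alternative quantities within the both class, or the quantity-based cross-price elasticity of protocol section 2.1, so that partial replacement is separated from add-on use.
4. Keep the analyses of total cigarettes and budget share, and describe them as aggregate evidence.

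The cost is one derived variable and one extra model, using the purchases that the marketplace task records. The drawback is that alternatives-only trials may be few at low cigarette prices, so intervals there will be wider. The SAP and protocol must also be reconciled on the product feature compared and the number of participants, so that the analysis is written for the conditions actually run.
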